APPENDIX X: PHARMACODYNAMIC/BIOMARKER STUDY FORM

COG Pt ID # _____ ACC # _____
Please do not write patient names on this form or on samples.

Cycle 1, Day 1 Date: |_|/|_|/|_|/|_| Body Surface Area: _____ m²

Dose Level: _____ mg/m² Total Weekly Dose per Nomogram: _____ mg

NOTE: To be accessioned for Exelixis.

Blood samples (5 mL each) will be obtained at baseline and prior to dose on Day 1, Day 21 (\pm 2 days) and Day 28 (\pm 2 days) of Cycle 1. Record the exact date and time each sample is drawn.

Blood Sample No.	Barcode # (from Sample Label)	Time Point	Scheduled Collection Time	Actual Date Sample Collected	Actual Time Sample Collected
1		Baseline/Pre-Study	Prior to first dose on Day 1	_ _ / _	_ _ _ : _ _
2		Cycle 1, Day 1	Prior to first dose on Day 1*	_ _ / _	_ _ _ : _ _
3		Cycle 1, Day 21 (\pm 2)	Prior to dose on Day 21 (\pm 2)*	_ _ / _	_ _ _ : _ _
4		Cycle 1, Day 28 (\pm 2)	Prior to dose on Day 28 (\pm 2)*	_ _ / _	_ _ _ : _ _

* Blood samples should be drawn within 1 hour prior to dose.

Sample Processing Procedures- Refer to PD Lab Manual for additional details

1. Draw 5 mL of whole blood into a pre-labeled 6-mL Vacutainer tube (refer to PD Kit provided by Exelixis).
2. Invert the collection tube gently at least 5 times.
3. Within 30 minutes of collection, separate the plasma fraction by centrifugation (1200 \times g for 10 minutes). A refrigerated centrifuge is preferred, and if available, should be set to 4°C.
4. Transfer the plasma to a 15 mL polypropylene tube and mix gently and thoroughly with a pipette. Be sure to avoid aspiration of cellular material near the buffy coat. Aliquot 0.5 mL into each of the 4 pre-labeled 1.2-mL cryovials. Distribute any extra plasma evenly between the vials.
5. Freeze plasma samples immediately (-70°C or colder). The samples must be stored on dry ice if a freezer is not immediately available.

Sample Shipping Procedures- Refer to [Appendix XII](#) for sample shipping guidelines.

One copy of this Biomarker Study Form should be uploaded into RAVE. A second copy should be sent with the samples to the lab at the address listed in [Appendix XII](#). Refer to Pharmacodynamic Lab Manual provided by Exelixis for additional details.

If this form will be used as a source document, the site personnel who collected the samples must sign and date this form below:

Signature: _____

Date: _____

APPENDIX XI: TISSUE STUDY FORM

COG Pt ID # _____ ACC # _____ Cycle 1, Day 1 Date: _____
Please do not write patient names on this form or on samples.

Body Surface Area: _____ m² Dose Level: _____ mg/m²

NOTE: To be accessioned for Exelixis.

Tumor Sample Labeling:

Samples should be labeled with the following information:

Protocol number: ADVL1211
Institution: _____
Patient ID #: _____
Accession #: _____
Sample Date: _____
Site of Acquired Tissue: _____
Number of Slides: _____
Barcode #: _____ (from Sample Label provided by Exelixis)
Tissue obtained at (check one option below):  Diagnosis  Relapse

Tumor Tissue:

Archival tumor tissue slides (10-15 unstained slides approximately 5 micron thickness on positively charged glass slides) from a formalin-fixed, paraffin-embedded tumor block will be shipped at room temperature .

Fill two to three 5-place slide containers with the slides and label each container with a Pharmacodynamics Sample Label (provided by Exelixis). Please indicate above the date of the sample, site of tissue acquisition and whether it was obtained at diagnosis or relapse. One copy of this form should be uploaded into RAVE.

Shipping Procedures- Refer to [Appendix XII](#) for sample shipping guidelines.

If this form will be used as a source document, the site personnel who collected the samples must sign and date this form below:

Signature: _____ Date: _____
(site personnel who collected samples)

APPENDIX XII: PACKAGING AND SHIPPING INSTRUCTIONS FOR PHARMACODYNAMIC AND ARCHIVAL TISSUE SAMPLES

Packaging Instructions:

1. Shipments should be scheduled after all samples have been collected from at least one subject. Samples may be batched for shipment after the end of cycle.
2. Once the pharmacodynamic and tissue samples are collected, the Pharmacodynamic Biomarker and Tumor Tissue CRFs and corresponding Study Forms (Appx [X-XI](#)) should be completed and uploaded into RAVE. An email notification must then be sent to the Study Research Coordinator. **The Study Research Coordinator will notify each site when the shipment may proceed.**
3. Shipment of Plasma Samples
 - a. Place the tubes into a sealable plastic bag (one subject per bag) surrounded by absorbent material.
 - b. Place the plastic bags into a suitable Styrofoam shipping container (e.g., ThermoSafe) and fill with enough dry ice for 2 days in transit (e.g., 8 pounds).
4. Shipment of Archival Tumor samples
 - a. Make sure the microscope slide holders are properly labeled and taped closed. Surround the slide holders with packing material such as bubble wrap and pack into a shipping box such that the samples cannot move.
5. The shipping address is:
Covance Biorepository Services
Attn: [name] – Biorepository/LTS Building 210
[name]
Greenfield, Indiana, 46140
[contact]

Include a copy of Pharmacodynamic/Biomarker Study Form ([Appendix X](#)) and Tissue Study Form ([Appendix XI](#)) along with the sample shipment.

Please **DO NOT** ship samples on a Thursday or Friday, or within 2 days of holiday.

**APPENDIX XIII: UNACCEPTABLE ENZYME INDUCING AND RECOMMENDED
NON-ENZYME INDUCING ANTICONVULSANTS**

Recommended Non-enzyme inducing anticonvulsants	
Generic Name	Trade Name
Gabapentin	Neurontin
Lamotrigine	Lamictal
Levetiracetam	Keppra
Tigabine	Gabitril
Topiramate	Topamax
Valproic Acid	Depakote, Depakene
Zonisamide	Zonegran

Unacceptable Enzyme inducing anticonvulsants	
Generic Name	Trade Name
Carbamazepine	Tegretol
Felbamate	Felbatol
Phenobarbital	Phenobarbital
Phenytoin	Dilantin
Primidone	Mysoline
Oxcarbazepine	Trileptal

APPENDIX XIV: PATIENT INSTRUCTIONS FOR TREATING DIARRHEA

Guidelines for the Treatment of Diarrhea

Institutional practice may be used in place of these guidelines.

Each family will be instructed to have antidiarrheal medication available and begin treatment at the first episode of poorly formed or loose stools or the earliest onset of bowel movements more frequent than normally expected for the patient. Patients will also be instructed to contact their physician if any diarrhea occurs. Patients will be given **loperamide** based on body weight. The doses and schedules for loperamide included here are higher than the standard but consistent with COG protocols D9802, P9761, ARST0121, and ADVL0918.

Be aware of your child's bowel movements. At the first sign they become softer than usual or if your child has any notable increase in the number of bowel movements over what is normal for him/her, begin taking loperamide (Imodium).

Please follow these directions carefully, using dosing guidelines below:

- Take _____ at the first sign of diarrhea.
- Continue taking _____ every 2 hours until the diarrhea slows or the normal pattern of bowel movements returns. Repeat the same doses and frequency if the diarrhea returns.
- Do not exceed _____ in a 24 hour period.
- Please call your doctor if you have any questions about taking loperamide, if your child's diarrhea is not under control after two days, or if he/she is feeling extremely weak, lightheaded, or dizzy.
- Make an extra effort to give your child lots of fluids (several glasses of pedialyte, fruit juices, soda, soup, etc.) while your child is participating in this study.
- Side effects may include tiredness, drowsiness or dizziness. If your child experiences these side effects, or if your child is urinating less frequently than usual, please contact your child's physician.
- Do not give your child any laxatives without consulting with his/her physician.

LOPERAMIDE DOSING RECOMMENDATIONS	
(NOTE: maximum dose of loperamide for adults is 16 mg/day)	
ALL patients: discontinue loperamide when the patient is no longer experiencing significant diarrhea.	
Weight (kg)	ACTION
<13 kg	Take 0.5 mg (one-half teaspoonful of the 1 mg/5 mL oral solution) after the first loose bowel movement, followed by 0.5 mg (one-half teaspoonful of the 1 mg/5 mL oral solution) every 3 hours. During the night, the patient may take 0.5 mg (one-half teaspoonful of the 1 mg/5 mL oral solution) every 4 hours. Do not exceed 4 mg per day.
≥ 13 kg to < 20 kg	Take 1 mg (1 teaspoonful of the 1 mg/5 mL oral solution or one-half capsule or tablet) after the first loose bowel movement, followed by 1 mg (one teaspoonful of the 1 mg/5 mL oral solution) every 3 hours. During the night, the patient may take 1 mg (one teaspoonful of the 1 mg/5 mL oral solution) every 4 hours. Do not exceed 6 mg per day.
≥ 20 kg to < 30 kg	Take 2 mg (2 teaspoonfuls of the 1 mg/5 mL oral solution or 1 capsule or tablet) after the first loose bowel movement, followed by 1 mg (one teaspoonful of the 1 mg/5 mL oral solution or one-half capsule or tablet) every 3 hours. During the night, the patient may take 2 mg (2 teaspoonfuls of the 1 mg/5 mL oral solution or 1 caplet) every 4 hours. Do not exceed 8 mg per day.
≥ 30 kg to < 43 kg	Take 2 mg (2 teaspoonfuls of the 1 mg/5 mL oral solution or 1 capsule or tablet) after the first loose bowel movement, followed by 1 mg (one teaspoonful of the 1 mg/5 mL oral solution or one-half capsule or tablet) every 2 hours. During the night, the patient may take 2 mg (2 teaspoonfuls of the 1 mg/5 mL oral solution or 1 capsule or tablet) every 4 hours. Do not exceed 12 mg per day.
Over 43 kg	Take 4 mg (4 teaspoonfuls of the 1 mg/5 mL oral solution or 2 capsules or tablets) after the first loose bowel movement, followed by 2 mg (2 teaspoonfuls of the 1 mg/5 mL oral solution or 1 capsule or tablet) every 2 hours. During the night, the patient may take 4 mg (4 teaspoonfuls of the 1 mg/5 mL oral solution or 2 capsules or tablets) every 4 hours. Do not exceed 16 mg per day.

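### The Appendix XIV family sheet prints a 2-hour loperamide interval for every child, but its own weight table gives 3 hours by day below 30 kg (minor internal inconsistency)

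*Combined protocol and SAP*

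**What the plan says.** Appendix XIV has two parts that a site uses together: a sheet addressed to the family and a loperamide dosing table by weight.

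On the sheet, the first dose, the repeat dose and the 24-hour maximum are blanks. The interval is not. The repeat dose is to be taken "every 2 hours until the diarrhea slows or the normal pattern of bowel movements returns", with no weight condition, and the same frequency is to be used again if diarrhea returns. The lead-in to these lines reads "Please follow these directions carefully, using dosing guidelines below".

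The table sets the daytime interval by weight. For children under 13 kg the first dose is "followed by 0.5 mg (one-half teaspoonful of the 1 mg/5 mL oral solution) every 3 hours". For 13 to <20 kg it is "followed by 1 mg (one teaspoonful of the 1 mg/5 mL oral solution) every 3 hours". The 20 to <30 kg row also gives 1 mg every 3 hours. The rows for 30 to <43 kg and over 43 kg give every 2 hours. Every row also allows a night-time dose every 4 hours, which the sheet does not mention, and states a daily maximum.

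The introduction to the appendix says loperamide is given according to body weight. It adds three qualifications: "Institutional practice may be used in place of these guidelines"; "Patients will also be instructed to contact their physician if any diarrhea occurs"; and "The doses and schedules for loperamide included here are higher than the standard but consistent with COG protocols D9802, P9761, ARST0121, and ADVL0918". The table heading adds a stopping rule: "discontinue loperamide when the patient is no longer experiencing significant diarrhea".

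**The concern.** The interval is the one dosing element on the sheet that a site cannot adapt to the child, yet the table makes it depend on weight. The sheet refers the reader to the table but does not say which interval applies when the two differ.

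Parents act on this instruction at home. Section 7.3 describes diarrhea as common with the study drug, and Sections 6.8 and 7.3 both direct sites to this appendix. Eligibility starts at age 2 (Section 4.1.1), so children under 30 kg can enroll, although the requirement to swallow intact tablets (Section 4.2.3) limits the youngest. What is at stake is supportive-care dosing in smaller children, not the trial's inference.

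**Working it through.** **Inputs**, all from Appendix XIV. The sheet's interval is 2 hours. First dose, daytime repeat, night allowance and daily maximum come from the table. The sheet's repeat dose is taken to be the table's daytime repeat dose, as a site would enter it.

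| Band | First dose | Table, day | Table, night | Daily maximum | Sheet interval agrees? |
|---|---|---|---|---|---|
| <13 kg | 0.5 mg | 0.5 mg every 3 h | 0.5 mg every 4 h | 4 mg | No |
| 13 to <20 kg | 1 mg | 1 mg every 3 h | 1 mg every 4 h | 6 mg | No |
| 20 to <30 kg | 2 mg | 1 mg every 3 h | 2 mg every 4 h | 8 mg | No |
| 30 to <43 kg | 2 mg | 1 mg every 2 h | 2 mg every 4 h | 12 mg | Yes |
| Over 43 kg | 4 mg | 2 mg every 2 h | 4 mg every 4 h | 16 mg | Yes |

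The sheet agrees with the table in 2 of 5 bands.

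**Frequency.** Below 30 kg the ratio of the sheet's daytime frequency to the table's is 3/2 = 1.5.

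**Hourly rate of repeat dosing** (repeat dose divided by interval), compared within the child's own band:

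- <13 kg: sheet 0.5/2 = 0.25 mg/h; table 0.5/3 = 0.167 by day and 0.5/4 = 0.125 by night.
- 13 to <20 kg: sheet 1/2 = 0.5 mg/h; table 1/3 = 0.333 by day and 1/4 = 0.25 by night.
- 20 to <30 kg: sheet 1/2 = 0.5 mg/h; table 1/3 = 0.333 by day and 2/4 = 0.5 by night.

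Below 20 kg the sheet's rate is above both rates in the band. For 20 to <30 kg it is above the daytime rate and equal to the night allowance.

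**Time to the daily maximum.** Assume continuous dosing from hour 0, the night option not used, and the maximum respected. The number of repeats that fit is (maximum − first dose) / repeat dose, and the last permitted dose falls at that number times the interval.

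- <13 kg: (4 − 0.5)/0.5 = 7 repeats; last dose at hour 7 × 2 = 14 on the sheet, 7 × 3 = 21 on the table.
- 13 to <20 kg: (6 − 1)/1 = 5 repeats; hour 10 against hour 15.
- 20 to <30 kg: (8 − 2)/1 = 6 repeats; hour 12 against hour 18.

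The total dose is the same under either interval. The allowance is used up earlier, leaving 10, 14 and 12 hours of the day with none, against 3, 9 and 6 hours at the table's interval.

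**The case against.** The best case on the other side is that the form, completed as intended, already contains the risk. The line for the daily maximum is on the same sheet. The clinician who fills in the doses must read the row that states the 3-hour interval. Families are told to contact the physician if any diarrhea occurs, treatment stops once diarrhea is no longer significant, and a site may use its own practice instead. All of this stands and is why the point is minor. None of it changes the printed interval or says which of the two governs.

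The appendix also says its schedules are above the standard and agree with four named group protocols. Whether the forms in those protocols carry the same 2-hour line cannot be checked here. Agreement with them would not reconcile two conflicting lines within this appendix.

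A reader might infer that the sheet leads to overdose. Without the maximum, 24 hours at 2-hour intervals (11 repeats) would give 0.5 + 11 × 0.5 = 6 mg, 1 + 11 × 1 = 12 mg and 2 + 11 × 1 = 13 mg, against limits of 4, 6 and 8 mg. The documents do not support that reading. It requires the family to ignore the maximum on the same sheet and to dose through the night without the diarrhea slowing. The table's own 3-hour interval, run the same way (7 repeats), gives 4, 8 and 9 mg, which also passes the limit in two of the three bands. The maximum, not the interval, controls the total.

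A reader might also infer that below 20 kg the sheet's rate exceeds every rate in the table. That is true only within the child's own band: the 30 to <43 kg daytime rate is 1/2 = 0.5 mg/h, equal to the sheet's rate for 13 to <20 kg.

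**Conclusion.** The inconsistency is certain and nothing in the documents resolves it; its consequence is small. Below 30 kg a correctly completed sheet still tells families to repeat loperamide 1.5 times as often by day as the table does. With the maximum filled in and followed, the excess is in frequency and in how soon the allowance runs out, not in the daily total.

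The timing figures rest on continuous dosing without the night option. The documents do not say how many patients weigh under 30 kg, so the number of families affected is unknown. Nor do they show that any child was harmed or given more than the daily limit. No endpoint, DLT rule or statistical quantity is affected. This is an internal inconsistency of minor severity.

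**What to change.** On the Appendix XIV family sheet, replace the printed 2-hour interval with `every ___ hours`, completed by the site from the child's weight band: 3 hours below 30 kg, 2 hours from 30 kg. The interval is then handled like the dose and daily-maximum blanks beside it. This is a one-line form correction with no effect on data collection, endpoints or sample size.

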APPENDIX XV: MEDICATIONS ASSOCIATED WITH PROLONGED QTc

For the most current list of medications, please refer to the following website: www.torsades.org.

1. Medications that prolong QTc

Generic name	Brand name
Amiodarone	Cordarone®
Arsenic trioxide	Trisenox®
Astemizole	Hismanal®
Azithromycin	Zithromax®
Bepridil	Vascor®
Chloroquine	Aralen®
Chlorpromazine	Thorazine®
Clarithromycin	Biaxin®
Disopyramide	Norpace®
Dofetilide	Tikosyn®
Domperidone	Motilium®
Droperidol	Inapsine®
Erythromycin	Erythrocin®
Flecainide	Tambocor®
Halofantrine	Halfan®

Generic name	Brand name
Haloperidol	Haldol®
Ibutilide	Corvert®
Mesoridazine	Serentil®
Methadone	Dolophine®
Moxifloxacin	Avelox®
Pentamidine	Pentam®
Pimozide	Orap®
Probucol	Lorelco®
Procainamide	Procan®
Quinidine	Quinaglute®
Sotalol	Betapace®
Sparfloxacin	Zagam®
Terfenadine	Seldane®
Thioridazine	Mellaril®
Vandetanib	Caprelsa®

2. Medications that may prolong QTc

Generic name	Trade name
Alfuzosin	Uroxatral®
Amantadine	Symmetrel®
Atazanavir	Reyataz®
Chloral hydrate	Noctec®
Clozapine	Clozaril®
Dolasetron	Anzemet®
Dronedarone	Multaq®
Eribulin	Halaven®
Escitalopram	Cipralex®
Escitalopram	Lexapro®
Famotidine	Pepcid®
Felbamate	Felbatrol®
Fingolimod	Gilenya®
Foscarnet	Foscavir®
Fosphenytoin	Cerebyx®
Gemifloxacin	Factive®
Granisetron	Kytril®
Iloperidone	Fanapt®
Indapamide	Lozol®
Isradipine	Dynacirc®
Lapatinib	Tykerb®
Levofloxacin	Levaquin®
Lithium	Lithobid®

Generic name	Trade name
Moexipril/HCTZ	Uniretic®
Nicardipine	Cardene®
Nilotinib	Tasigna®
Octreotide	Sandostatin®
Ofloxacin	Floxin®
Ondansetron	Zofran®
Oxytocin	Pitocin®
Paliperidone	Invega®
Quetiapine	Seroquel®
Ranolazine	Ranexa®
Risperidone	Risperdal®
Roxithromycin	Rulide®
Sertindole	Serdolect®
Sertindole	Serlect®
Sunitinib	Sutent®
Tacrolimus	Prograf®
Tamoxifen	Nolvadex®
Telithromycin	Ketek®
Tizanidine	Zanaflex®
Vardenafil	Levitra®
Venlafaxine	Effexor®
Voriconazole	VFend®
Ziprasidone	Geodon®

APPENDIX XVI: CTEP AND CTSU REGISTRATION PROCEDURES

Food and Drug Administration (FDA) regulations and National Cancer Institute (NCI) policy require all individuals contributing to NCI-sponsored trials to register and to renew their registration annually. To register, all individuals must obtain a Cancer Therapy Evaluation Program (CTEP) Identity and Access Management (IAM) account (<https://ctepcore.nci.nih.gov/iam>). In addition, persons with a registration type of Investigator (IVR), Non-Physician Investigator (NPIVR), or Associate Plus (AP) (i.e., clinical site staff requiring write access to OPEN, RAVE, or TRIAD or acting as a primary site contact) must complete their annual registration using CTEP's web-based Registration and Credential Repository (RCR) (<https://ctepcore.nci.nih.gov/rcr>). Documentation requirements per registration type are outlined in the table below.

Documentation Required	IVR	NPIVR	AP	A
FDA Form 1572	✓	✓		
Financial Disclosure Form	✓	✓	✓	
NCI Biosketch (education, training, employment, license, and certification)	✓	✓	✓	
HSP/GCP training	✓	✓	✓	
Agent Shipment Form (if applicable)	✓			
CV (optional)	✓	✓	✓	

An active CTEP-IAM user account and appropriate RCR registration is required to access all CTEP and CTSU (Cancer Trials Support Unit) websites and applications. In addition, IVRs and NPIVRs must list all clinical practice sites and IRBs covering their practice sites on the FDA Form 1572 in RCR to allow the following:

- Added to a site roster
- Assigned the treating, credit, consenting, or drug shipment (IVR only) tasks in OPEN
- Act as the site-protocol PI on the IRB approval
- Assigned the Clinical Investigator (CI) role on the Delegation of Tasks Log (DTL).

Additional information can be found on the CTEP website at <<https://ctep.cancer.gov/investigatorResources/default.htm>>. For questions, please contact the RCR **Help Desk** by email at <[contact]>.

CTSU Registration Procedures

This study is supported by the NCI Cancer Trials Support Unit (CTSU).

IRB Approval:

Each investigator or group of investigators at a clinical site must obtain IRB approval for this protocol and submit IRB approval and supporting documentation to the CTSU Regulatory Office before they can be approved to enroll patients. Assignment of site registration status in the CTSU Regulatory Support System (RSS) uses extensive data to make a determination of whether a site has fulfilled all regulatory criteria including but not limited to the following:

- An active Federal Wide Assurance (FWA) number
- An active roster affiliation with the Lead Network or a participating organization
- A valid IRB approval
- Compliance with all protocol specific requirements.

In addition, the site-protocol Principal Investigator (PI) must meet the following criteria:

- Active registration status
- The IRB number of the site IRB of record listed on their Form FDA 1572
- An active status on a participating roster at the registering site.

Sites participating on the NCI CIRB initiative that are approved by the CIRB for this study are not required to submit IRB approval documentation to the CTSU Regulatory Office. For sites using the CIRB, IRB approval information is received from the CIRB and applied to the RSS in an automated process. Signatory Institutions must submit a Study Specific Worksheet for Local Context (SSW) to the CIRB via IRBManager to indicate their intent to open the study locally. The CIRB's approval of the SSW is then communicated to the CTSU Regulatory Office. In order for the SSW approval to be processed, the Signatory Institution must inform the CTSU which CIRB-approved institutions aligned with the Signatory Institution are participating in the study.

Requirements for ADVL1211 Site Registration:

- IRB approval (For sites not participating via the NCI CIRB; local IRB documentation, an IRB-signed CTSU IRB Certification Form, Protocol of Human Subjects Assurance Identification/IRB Certification/Declaration of Exemption Form, or combination is accepted)
- For applicable studies with a radiation and/or imaging (RTI) component, the enrolling site must be aligned to a RTI provider. To manage provider associations access the Provider Association tab on the CTSU website at <https://www.ctsu.org/RSS/RTFProviderAssociation>, to add or remove associated providers. Sites must be linked to at least one IROC credentialed provider to participate on trials with an RT component. Enrolling sites are responsible for ensuring that the appropriate agreements are in place with their RTI provider, and that appropriate IRB approvals are in place.

Submitting Regulatory Documents:

Submit required forms and documents to the CTSU Regulatory Office, where they will be entered and tracked in the CTSU RSS.

Regulatory Submission Portal: www.ctsu.org (members' area) → Regulatory Tab →Regulatory

Submission

When applicable, original documents should be mailed to:

CTSU Regulatory Office
[name]
Philadelphia, PA 19103

Institutions with patients waiting that are unable to use the Portal should alert the CTSU Regulatory Office immediately at [name] in order to receive further instruction and support.
